### 6.4.1 Concomitant Medications with Venetoclax

Venetoclax is predominantly metabolized by CYP3A4/5. Concomitant use of venetoclax with strong inhibitors of CYP3A at initiation and during ramp-up phase is contraindicated. For patients who have completed the ramp-up phase and are on a steady daily dose, reduce the dose by at least 75% when used concomitantly with strong CYP3A inhibitors. Resume the venetoclax dose that was used prior to initiating the CYP3A inhibitor 2 to 3 days after discontinuation of the inhibitor.

Avoid concomitant use of moderate CYP3A inhibitors or P-gp inhibitors. If a moderate CYP3A inhibitor or a P-gp inhibitor must be used, reduce the dose by at least 50%. Resume the dose that was used prior to initiating the CYP3A inhibitor or P-gp inhibitor 2 to 3 days after discontinuation of the inhibitor. If a narrow therapeutic index P-gp substrate must be used, it should be taken at least 6 hours before venetoclax.

Avoid concomitant use with strong CYP3A inducers or moderate CYP3A inducers.

Venetoclax may cause a significant increase in Cmax and AUC of warfarin. International normalized ratio (INR) should be monitored closely in patients receiving warfarin.

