#### 6.4.1.1 Venetoclax Dose Adjustments with Common Antifungals and Other CYP3A Inhibitors

The dose of venetoclax should be adjusted to the following doses if taken with these antifungal medications:

Posaconazole:

Ramp-up Day 1- 20 mg venetoclax

Ramp-up Day 2- 50 mg venetoclax

Day 3 and onward- 70 mg venetoclax

Moderate CYP3A Inhibitors (ex. Fluconazole/Isavuconazole):

Ramp-up Day 1- 50 mg venetoclax

Ramp-up Day 2- 100 mg venetoclax

Day 3 and onward- 200 mg venetoclax

Strong CYP3A Inhibitors (ex. Voriconazole):

Ramp-up Day 1- 20 mg venetoclax

Ramp-up Day 2- 50 mg venetoclax  
Day 3 and onward- 100 mg venetoclax

Because there is a potential for interaction of nivolumab, decitabine, and venetoclax with other concomitantly administered drugs, the case report form must capture the concurrent use of all other drugs, over-the-counter medications, or alternative therapies. The Principal Investigator should be alerted if the patient is taking any agent known to affect or with the potential for drug interactions. The study team should check a frequently-updated medical reference for a list of drugs to avoid or minimize use of. Appendix D (Patient Drug Interactions Handout and Wallet Card) should be provided to patients if available.

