#### 6.4.2 Prophylaxis and Management of Tumor Lysis Syndrome

Upon treatment of hematologic malignancies there is a potential for TLS, especially in those with elevated pretreatment LDH levels, elevated leukocyte count, renal dysfunction, and dehydration. To mitigate the risk for TLS, all patients on this study will be considered high risk for TLS and will receive tumor lysis prophylaxis, including hydration (e.g., oral, intravenous) and treatment with an agent to reduce the uric acid level (e.g., allopurinol, rasburicase). Patients will not be eligible for study if WBC >25,000 as per current recommendations of venetoclax with hypomethylating agents per the FDA label.

It is recommended that all subjects receive the following TLS prophylaxis measures:

- Administration of an oral uric acid reducer (such as allopurinol 300 mg/day) prior to initial study therapy administration (ideally at least 72 hours prior when possible) and continued until each subject has completed a week at their highest dose level of venetoclax.
- Chemistry and hematology laboratory tests to be performed the morning of the first dose of venetoclax. The investigator's decision to proceed with venetoclax treatment initiation will be based on these laboratory values.
- Rasburicase (given at a flat dose of 6 mg IV x 1, or per institutional standards) must be administered per institutional guidelines for subjects with elevated uric acid level at baseline ( $>$  ULN) as prophylaxis prior to the initial dose of venetoclax. For subjects with a contraindication to rasburicase (i.e., glucose-6-phosphate dehydrogenase [G6PD] deficiency), the TLS risk-mitigation plan must be reviewed with the Overall PI.
- Chemistry laboratory tests must be performed STAT at least at the following time points: pre-dose (within 4 hours before venetoclax administration), and every 12 hours during the venetoclax ramp-up period. These laboratory values must be reviewed in real time by the investigator. Pre-dose laboratory values will be collected and used as baseline to assess potential electrolyte abnormalities occurring post venetoclax administration.

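### Section 6.4.1 contraindicates venetoclax with strong CYP3A inhibitors during ramp-up, while 6.4.1.1 prescribes ramp-up doses with them

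*Combined protocol and SAP*

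**What the plan says.** Section 6.4.1 gives the general rule on strong inhibitors: "Concomitant use of venetoclax with strong inhibitors of CYP3A at initiation and during ramp-up phase is contraindicated". It makes no exception. Once ramp-up is complete, a strong inhibitor is allowed if the venetoclax dose is cut by 75% or more. Moderate inhibitors are discouraged but not barred at any stage: "If a moderate CYP3A inhibitor or a P-gp inhibitor must be used, reduce the dose by at least 50" percent. When an inhibitor is withdrawn, the rule is: "Resume the venetoclax dose that was used prior to initiating the CYP3A inhibitor 2 to 3 days after discontinuation of the inhibitor".

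Section 6.4.1.1 then lists doses by co-medication. The block headed "Strong CYP3A Inhibitors (ex. Voriconazole" and the separate posaconazole block both open with "Ramp-up Day 1- 20 mg venetoclax" and give 50 mg on Day 2. From Day 3 they give 100 mg and 70 mg respectively. The block headed "Moderate CYP3A Inhibitors (ex. Fluconazole/Isavuconazole" gives 50, 100 and 200 mg.

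Other parts of the document bear on which rule is meant:

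- The venetoclax footnote to the regimen table in Section 6.1 sends the reader to 6.4.1.1 for dosing with CYP3A inhibitors.
- Section 2.3.2 says doses will be adjusted, following the FDA label, for moderate or strong inhibitors, but cites 6.3.1 and 6.3.1.1.
- Footnote V of the Section 11 calendar links ramp-up over Days 1-3 or 1-4 to inhibitor use and also cites 6.3.1. That number now belongs to the definition of patients evaluable for toxicity.
- Section 9.3 groups posaconazole and voriconazole as strong inhibitors.

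**The concern.** The ramp-up rows for posaconazole and voriconazole apply only in the situation that 6.4.1 forbids, so the two texts cannot both be followed. A site reading 6.4.1 would not give venetoclax alongside the azole. A site reading 6.4.1.1 would continue the azole and give 20 mg. Neither would be deviating from the text it read.

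The situation is foreseeable. Section 2.5.4 describes antifungals as routine companions of venetoclax and as moderate-to-strong CYP3A4 inhibitors. The baseline sample in Section 5.1 is labelled as taken before venetoclax or azole. Nothing in Sections 3.1 or 3.2 excludes a patient on a strong inhibitor.

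What is at stake is the first dose of a drug with a tumour lysis risk, in a trial where Section 6.4.2 treats every patient as high risk for that event. A related gap follows. Section 6.4.1 says what is forbidden but not what to do instead, and it sets no interval between stopping a strong inhibitor and a first dose of venetoclax. Its 2 to 3 day wait is written for returning to a dose used before the inhibitor was started. A patient who begins venetoclax while on the inhibitor has never had such a dose.

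**Working it through.** No power or error-rate calculation is involved. The check asks how far the two sections disagree.

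**Step 1: standard ramp.** Sections 2.3.2 and 6.1 give 100 mg on Day 1, 200 mg on Day 2 and 400 mg from Day 3.

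**Step 2: reductions implied by 6.4.1.1.** Reduction = 1 - (tabulated dose / standard dose).

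| Co-medication | Day 1 | Day 2 | Day 3 onward |
|---|---|---|---|
| Posaconazole | 1 - 20/100 = 80% | 1 - 50/200 = 75% | 1 - 70/400 = 82.5% |
| Other strong (e.g. voriconazole) | 1 - 20/100 = 80% | 1 - 50/200 = 75% | 1 - 100/400 = 75% |
| Moderate | 1 - 50/100 = 50% | 1 - 100/200 = 50% | 1 - 200/400 = 50% |

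**Step 3: compare with the rules in 6.4.1.** The minimum cut after ramp-up is 75% for strong inhibitors; 75% and 82.5% both meet it. The minimum for moderate inhibitors is 50%, and every moderate entry meets it. The sections therefore agree on moderate inhibitors throughout and on strong inhibitors after ramp-up. They disagree on one matter: whether a strong inhibitor may be given with venetoclax during ramp-up.

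**Step 4: length of the conflict.** Section 6.4.1.1 labels only Days 1 and 2 as ramp-up. Section 2.3.2 and calendar footnote V extend ramp-up to Day 3. The conflict therefore lasts two or three days, depending on the definition.

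**Step 5: the instruction on Day 1 for a patient on a strong azole.**

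- Under 6.4.1: no co-administration.
- Under 6.4.1.1: 20 mg with the azole continued.

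**Step 6: is precedence stated?** No sentence says that one section overrides the other. The regimen-table footnote names 6.4.1.1, and 2.3.2 speaks of adjusting doses rather than excluding strong inhibitors. Both point towards 6.4.1.1 as the working rule. Footnote V points the same way, but through an outdated number. The 10 mg tablet in Section 8.3.2, which the 20 mg and 70 mg doses require, adds little because it is listed as a strength in which a commercial product is supplied.

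**Step 7: footnote V.** Every schedule in 6.1 and 6.4.1.1 reaches its final dose on Day 3, so the alternative of Days 1-4 matches none of them.

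**The case against.** The strongest reply is that the intent can be worked out. Section 6.4.1.1 is the more specific text, it sits under 6.4.1, and the regimen table refers to it by number. This stands as evidence of intent, and the fix builds on it. It does not turn an unqualified contraindication into a conditional one, and prescribers should not have to infer that a stated contraindication does not apply.

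A second reply is that the consequences are bounded. Chemistry is checked "every 12 hours during the venetoclax ramp-up period", results are reviewed in real time, and the next ramp-up dose waits for the 24-hour values. In addition, "The Principal Investigator should be alerted if the patient is taking any agent known to affect or with the potential for drug interactions". Venetoclax PK sampling (Cycle 1 Day 14) and the DLT window (from Cycle 1 Day 15) both come after ramp-up. All of this is correct and limits the effect on the trial's results. It does not tell a site which rule to follow, and an event during ramp-up would fall before the DLT window opens.

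Two stronger readings are tempting. A reader might infer that the Day 1 dose for such a patient is open between 20, 50 and 100 mg, or none at all. The documents do not support that. With the strong azole continued, 20 mg is the only tabulated dose. The 50 mg dose belongs to moderate inhibitors and 100 mg to patients on no inhibitor, so those are the intended doses for different co-medication. Section 6.4.1 bars concomitant use; it does not order venetoclax to be withheld. A reader might also divide the standard doses by the reduced ones and call the ratio a dosing error. That compares treatment with and without an inhibitor, where different nominal doses are intended, and says nothing about exposure.

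On the resumption rule, 400 mg could fairly be taken as the scheduled target. That still leaves the timing and steps unstated when the inhibitor stops before or during ramp-up.

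**Conclusion.** The contradiction is real and should be corrected. For a patient taking posaconazole, voriconazole or another strong CYP3A inhibitor at Day 1, the protocol both forbids co-administration with venetoclax and prescribes 20 mg. The conflict is confined to two or three days per affected patient. The sections agree on strong inhibitors after ramp-up and on moderate inhibitors throughout.

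Section 6.4.1.1 is probably the intended rule, but that is an inference from the regimen-table footnote and Section 2.3.2. Which section is clinically right depends on the label that 2.3.2 cites, which is not among the documents. The number of patients who would be on a strong azole during ramp-up is not given, so no frequency can be attached. The response rule, the sample size and the DLT definition are unaffected.

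**What to change.** 1. The sponsor checks 6.4.1.1 against the label that Section 2.3.2 cites.
2. If the label supports it, replace the contraindication sentence in 6.4.1 with: 'Strong CYP3A inhibitors may be used at initiation and during ramp-up only at the doses in 6.4.1.1 (posaconazole 20/50/70 mg; other strong inhibitors 20/50/100 mg).'
3. If the label does not support it, keep the contraindication and delete the posaconazole and strong-inhibitor ramp-up rows from 6.4.1.1, leaving the doses from Day 3 onward for use after ramp-up.
4. In either case, the sponsor states how venetoclax is started or increased when a strong inhibitor is stopped shortly before or during ramp-up, consistent with the 2 to 3 day interval already in 6.4.1. The schedule itself is a clinical decision for the sponsor.
5. Correct the references in Section 2.3.2 and calendar footnote V from 6.3.1 and 6.3.1.1 to 6.4.1 and 6.4.1.1, and remove 'or 1-4' from footnote V.

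The cost is a label check and a few sentences at the next amendment. No change to sample size, endpoints or analysis is needed.

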#### 6.4.1.1 Venetoclax Dose Adjustments with Common Antifungals and Other CYP3A Inhibitors

The dose of venetoclax should be adjusted to the following doses if taken with these antifungal medications:

Posaconazole:

Ramp-up Day 1- 20 mg venetoclax

Ramp-up Day 2- 50 mg venetoclax

Day 3 and onward- 70 mg venetoclax

Moderate CYP3A Inhibitors (ex. Fluconazole/Isavuconazole):

Ramp-up Day 1- 50 mg venetoclax

Ramp-up Day 2- 100 mg venetoclax

Day 3 and onward- 200 mg venetoclax

Strong CYP3A Inhibitors (ex. Voriconazole):

Ramp-up Day 1- 20 mg venetoclax

Ramp-up Day 2- 50 mg venetoclax  
Day 3 and onward- 100 mg venetoclax

Because there is a potential for interaction of nivolumab, decitabine, and venetoclax with other concomitantly administered drugs, the case report form must capture the concurrent use of all other drugs, over-the-counter medications, or alternative therapies. The Principal Investigator should be alerted if the patient is taking any agent known to affect or with the potential for drug interactions. The study team should check a frequently-updated medical reference for a list of drugs to avoid or minimize use of. Appendix D (Patient Drug Interactions Handout and Wallet Card) should be provided to patients if available.

#### 6.4.2 Prophylaxis and Management of Tumor Lysis Syndrome

Upon treatment of hematologic malignancies there is a potential for TLS, especially in those with elevated pretreatment LDH levels, elevated leukocyte count, renal dysfunction, and dehydration. To mitigate the risk for TLS, all patients on this study will be considered high risk for TLS and will receive tumor lysis prophylaxis, including hydration (e.g., oral, intravenous) and treatment with an agent to reduce the uric acid level (e.g., allopurinol, rasburicase). Patients will not be eligible for study if WBC >25,000 as per current recommendations of venetoclax with hypomethylating agents per the FDA label.

It is recommended that all subjects receive the following TLS prophylaxis measures:

- Administration of an oral uric acid reducer (such as allopurinol 300 mg/day) prior to initial study therapy administration (ideally at least 72 hours prior when possible) and continued until each subject has completed a week at their highest dose level of venetoclax.
- Chemistry and hematology laboratory tests to be performed the morning of the first dose of venetoclax. The investigator's decision to proceed with venetoclax treatment initiation will be based on these laboratory values.
- Rasburicase (given at a flat dose of 6 mg IV x 1, or per institutional standards) must be administered per institutional guidelines for subjects with elevated uric acid level at baseline ( $>$  ULN) as prophylaxis prior to the initial dose of venetoclax. For subjects with a contraindication to rasburicase (i.e., glucose-6-phosphate dehydrogenase [G6PD] deficiency), the TLS risk-mitigation plan must be reviewed with the Overall PI.
- Chemistry laboratory tests must be performed STAT at least at the following time points: pre-dose (within 4 hours before venetoclax administration), and every 12 hours during the venetoclax ramp-up period. These laboratory values must be reviewed in real time by the investigator. Pre-dose laboratory values will be collected and used as baseline to assess potential electrolyte abnormalities occurring post venetoclax administration.
- If any significant laboratory changes are observed within the first 24 hours after initiation of dosing, see Appendix C (Recommendations for Initial Management of Electrolyte Abnormalities and Prevention of Tumor Lysis Syndrome [TLS]), for additional laboratory assessments and management guidelines. If aggressive correction of electrolytes abnormalities was performed, the subsequent dose of venetoclax can only be given when electrolytes have been stable without any further treatment for approximately 24 hours.
- Hematology laboratory tests will be performed pre-dose (within approximately 4 hours before venetoclax administration), and approximately 24 hours post-dose after the first dose of venetoclax.
- During the dose ramp-up period, the subsequent dose should not be administered until the 24

hours post-dose laboratory values are reviewed by the investigator.

\* All laboratory assessments may be taken within +/- 2 hour window, and 24 hour laboratory assessments within a +/-3 hour window, if necessary.

## 6.5 Duration of Therapy

In the absence of treatment delays due to adverse event(s), treatment may continue until one of the following criteria applies:

- Disease progression/loss of response
- Bone marrow/stem cell transplantation
- Intercurrent illness that prevents further administration of treatment
- Unacceptable adverse event(s)
- Patient decides to withdraw from the study
- General or specific changes in the patient's condition render the patient unacceptable for further treatment in the judgment of the investigator
- Clinical progression
- Patient non-compliance
- Pregnancy
  - All women of child bearing potential should be instructed to contact the investigator immediately if they suspect they might be pregnant (e.g., missed or late menstrual period) at any time during study participation.
  - The investigator must immediately notify CTEP in the event of a confirmed pregnancy in a patient participating in the study.
- Termination of the study by sponsor
- The drug manufacturer can no longer provide the study agent

The reason(s) for protocol therapy discontinuation, the reason(s) for study removal, and the corresponding dates must be documented in the Case Report Form (CRF).

### 6.5.1 Duration of Therapy in cases of CR

If the patient achieves a CR/CRi, even if MRD negative, the patient should continue on therapy as long as none of the above instances in 6.5 occurs. However, venetoclax may be interrupted, and the subsequent cycle of decitabine may be delayed to allow for absolute neutrophil count recovery from day 29 of current cycle until absolute neutrophil count reached at least 500/ $\mu$ L or

up to 14 days, then a bone marrow biopsy should be done to assess for continued CR/CRi. If patient remains in CR/CRi then dose reductions can occur as follows. For recurrent Grade 4 neutropenia and thrombocytopenia that lasts >6 weeks from Day 1 of cycle: first dose reduction will be to decrease venetoclax to 14 days (days 1-14 of the cycle), the second dose reduction will be to decreased to 7 days (days 1-7 of the cycle), the third dose reduction will be to reduce decitabine to 4 days (days 1-4 of the cycle), and the fourth/final dose reduction will be to reduce decitabine to 3 days (days 1-3 of the cycle). If Grade 4 thrombocytopenia and neutropenia recurs after all of these four dose reductions and lasting >56 days, patient will be taken off study.

## **6.6 Duration of Follow-Up**

Patients will be followed for up to 3 years after initiation of therapy or until death, whichever occurs first. Patients removed from study for unacceptable adverse event(s) will be followed until resolution or stabilization of the adverse event.

# **7. DOSING DELAYS/DOSE MODIFICATIONS**

## **7.1 Dose Delays/Modifications for DLT**

Study treatment (all three drugs) will be held for any patients experiencing a DLT.

Non-hematologic DLT: Patients may restart therapy when the adverse event recovers to CTCAE  $\leq$ grade 1 or to the patient's baseline values. If study treatment is restarted and another non-hematologic DLT is encountered, the patient must be removed from the study.

Hematologic DLT: After the 42 day period and confirmed hematologic DLT: If peripheral blasts are absent AND the bone marrow blasts are less than 5%, then the patient may restart study treatment with decrease of decitabine to 5 days from 10 days of therapy.

If treatment is delayed >6 weeks for an adverse event the patient must be permanently discontinued from study therapy.

Patients requiring > two dose delays for the same event should go off protocol therapy.

Please see specific modifications for Nivolumab (Section 7.3)

Drugs may be resumed per protocol. If a specific agent (e.g. decitabine or nivolumab or venetoclax) is permanently discontinued for toxicity, the other two agents may be continued on study. Decitabine and venetoclax doses should not be reduced following toxicity and dose interruption, they should continue at the same dose as stated in the protocol.

### **7.1.1 Dose Delays/Modifications for other adverse events**

All three study drugs will be held for adverse events requiring interruption until the toxicity can be evaluated, then resumed unless a drug needs to be permanently discontinued.

## **7.2 Dose modifications of Decitabine and Venetoclax for non-DLTs**

Subjects who experience a  $\geq$  grade 3 non-hematologic toxicity with 10 days of decitabine in the first cycle will have their dose reduced to 5 days in the second cycle.

Non-hematologic due to Decitabine or Venetoclax: Any subject who experiences a non-hematological AE related to the agent of Grade 3 or 4 that is an escalation from his or her status at baseline should have the agent temporarily held until the toxicity Grade returns to less than Grade 3. The agent should be permanently discontinued if the non-hematological toxicity persists as Grade 3 or 4 for more than 21 days, despite the temporary interruption of the agent and patients should be taken off treatment with this agent.

Hematologic AE due to decitabine or venetoclax: Decitabine and/or venetoclax doses should not be reduced following toxicity and dose interruption. Dose reductions of decitabine and venetoclax are allowed in the following manner. For recurrent Grade 4 non that lasts  $>6$  weeks from Day 1 of cycle: first dose reduction will be to decrease venetoclax to 14 days (days 1-14 of the cycle), the second dose reduction will be to decreased to 7 days (days 1-7 of the cycle), the third dose reduction will be to reduce decitabine to 4 days (days 1-4 of the cycle), and the fourth/final dose reduction will be to reduce decitabine to 3 days (days 1-3 of the cycle). If Grade 4 thrombocytopenia and neutropenia recurs after all of these four dose reductions and lasting  $>56$  days, patient will be taken off study.

### **7.3 Missed doses of Decitabine and Venetoclax**

Decitabine: If decitabine is missed/held, it may be restarted within 48 hours from time of missed dose, and the missed days can be made up. If longer than this period, patients will wait for further therapy until next cycle of treatment.

Venetoclax: If a dose is missed by less than 8 hours, take the missed dose right away and take the next dose as usual. If a dose is missed by more than 8 hours, the patient should wait and take the next dose at the usual time. Patients should not take an additional dose if they vomit after taking venetoclax. They should take the next dose at the usual time the following day. If a dose is vomited within one hour of ingestion, it will be considered a missed dose and recorded as such on the patient diary. The dose will not be repeated that same day but the patient will follow regular schedule starting the next study dosing day. If vomiting occurs more than 1 hour after dosing, it will still be considered a complete dose.

